### 8.3 Study procedures

The flow of the participants throughout the study is visualized in Figure 1, in paragraph 3.3. In this section, each step is explained in more detail.

#### **Step 1: Screening – Week 0**

Before the inclusion starts, therapists are asked whether they want to participate. In each clinic of the participating organizations, the goal is to involve at least three therapists that want to participate in the study. This number has been discussed with representatives of the four participating organizations and is viewed as feasible.

When a patient is enrolled in treatment, a ‘multidisciplinair overleg’ (MDO) always takes place in which the case is discussed and a plan for treatment is created. If the patient is allocated to a participating therapist, the treatment team that participates in the MDO discusses whether the patient is eligible for participation in this study based on the in- and exclusion criteria. If this is the case, researchers are notified. This entire process is supported by the office managers of the clinic: they remind therapists about the study before the MDO and notify the researchers.

#### **Step 2: Informing patient – Week 8 – 10**

Eight weeks after treatment has started, the therapist first introduces the study by means of a short explanation. The patient also receives a short information folder with information about the study. If this is the case, the patient will sign a consent form to indicate that they are willing to be contacted by one of the researchers, and enters their contact details and the preferred way of being contacted: by e-mail or phone. Therapists are reminded by the office manager to hand these materials and invite patients.

There are multiple reasons for the ‘waiting time’ of approximately 8 weeks between screening and informing. First of all, therapists indicate that patients receive a lot of information during the first weeks of their treatment and have to fill out a lot of questionnaires that are part of standard procedures in forensic mental healthcare. Participating in the study is expected to be quite overwhelming during this initial phase of treatment. Second, therapists indicate that it is important to take some time to build a therapeutic relationship before starting with an internet-based intervention, which is especially relevant due to the often low treatment motivation of forensic psychiatric patients. Third, it often happens that when patients are enrolled in treatment, there are a lot of urgent problems that require attention: some more practical, e.g. homelessness, some more psychological, e.g. high levels of anxiety or denial of problems. This can make the first phase of treatment quite chaotic. In order to ensure that internet-based interventions are introduced at the right time, inclusion is initiated around week 8. If it is not possible or feasible to introduce the study in

week 8 due to practical or treatment-related reasons, the therapist can also inform the patient up until, but no later than week 10.

### ***Step 3: Inclusion and informed consent – Week 8-11***

If the patient agrees to be contacted by the researcher, the researcher will contact them via their preferred way of communication, as indicated on the initial consent form. The patient is asked to participate by the researchers and not by the therapist to prevent that the patient feels obliged to participate if their therapist asks them – which is especially relevant for patients who follow treatment as part of a sentence. The patient will receive information about the goal and relevance of the study, the required effort, the rewards for participating, the consequences of randomization, and the nature of the internet-based intervention. The letter that contains all this information might be difficult to understand, so a short summary in simple language is added to make sure all patients are able to understand the goal and means of this study. Also a short video will be made to ensure that all the information is received and understood. The researcher will clearly communicate that during the data collection period, patients in the control group will not be able to use any of internet-based interventions offered by Minddistrict. However, once the study is finished, the patient can use the intervention. Consequently, if a patient is extremely motivated to use an internet-based intervention, they can decide not to participate in the study. The patient also will be given multiple opportunities to ask questions and to think five days about whether to participate. If it is possible for the researcher to visit the patient in real life at the treatment location, informed consent will be provided in person, after a waiting period of at least five days. If this is not possible, the informed consent form will be sent to the patient via post, after which a signed form can be returned by the patient via an included, stamped envelope. However, due to the psychosocial problems of this target group, it might not be possible or desirable for all patients to receive the informed consent form via post, for example because they don't have a fixed living address at that point in time, or because they don't want their housemates to know about participation in the study and/or in forensic care in general. If this is the case, and if both other options are not feasible, the informed consent will be e-mailed to the patient, after which they have time to read it. After five days, verbal informed consent will be obtained via a recorded videoconferencing session. In this way, the process of informed consent is adapted to the characteristics of the patient.

Throughout the entire process, it will be clearly communicated that participating in this study does not affect the patient's treatment progress or the evaluation of the therapist. It will also be clearly stated that the patient can decide to withdraw from the intervention and/or study at any point in treatment, without any consequences - other than not receiving the financial reimbursement that is part of the study.

**Step 4: Baseline assessment (T0) – Week 11**

Before they start with the intervention - thus before they are allocated to a condition - all participants will be sent a link to the self-report questionnaires by the researcher to assess self-efficacy, aggression, treatment readiness and to ask several short questions about sociodemographic variables. These questionnaires will be filled out online via the designated program Qualtrics. The patient is asked to fill out these questionnaires in their own time, but as soon as possible, preferably on the same day. If the patient has not filled out these questionnaire, an automated reminder will be sent after two days. If after that, the patient still did not fill out the questionnaires, the patient is contacted by the researcher via e-mail after five days, to remind them of filling out the questionnaires. If after those two reminders the patient has not completed the questionnaire yet, their therapist is contacted. In the upcoming session, the therapist will the patient for the reason for not completing the questionnaires. If this is due to for example difficulties with answering the questions, the researcher will contact the patient and fill the questionnaires out together. If the patient indicates that they do not want to fill out the questionnaire due to any other reason, the therapist will discuss if participation in the study is still an option.

Besides the self-report questionnaires, the risk assessment instrument FARE will be administered by the therapist as part of standard treatment. As mentioned before, because the FARE is embedded in standardized structures of the organization, it might be that this risk assessment instrument is administered several weeks before the questionnaires.

In this week, the therapist will also receive a short questionnaire via Qualtrics about background information regarding the patient (inpatient clinic in which the patient is treated, the main treatment goal, type of offense, and diagnoses).

**Step 5: Randomization and start intervention – Week 12**

Directly after the patient has provided informed consent, the patient is randomized by the researcher. This is communicated to the therapist, who will let the patient know whether they will start with the intervention 'Aggression' or if they will participate in the control group.

After the first session of the internet-based intervention is finished, the TWEETS will be administered to participants in the experimental group via the Minddistrict platform, because the TWEETS is integrated in the intervention.

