### 3.3 Overview of the study design

A schematic overview of the participant flow throughout the RCT, from screening up until follow-up assessment, is provided in Figure 1. The study design is briefly explained after the figure; a more detailed description of the procedure is provided in section 8.3.

The flow of the participants throughout the RCT is visualized in Figure 1. The first step, therapists will first **screen** the patients on suitability when they are first discussed in a 'multidisciplinary consultation' [multidisciplinair overleg; MDO]. Once the patient has been deemed suitable for participation, the therapists wait 8 weeks before **introducing** the study to the patient and asks for their consent to be contacted by a researcher. The main reason for not directly informing the patients during their intake or initial treatment sessions, is that patients already receive a lot of information at the beginning of their treatment, and thus often feel overwhelmed. Additionally, in practice, Minddistrict is often introduced later in the treatment process, because it often takes time to build a good therapeutic relationship, which is seen as a necessary requirement for starting with blended treatment, especially in a population known for its low treatment motivation.

If the patient agrees to be contacted by a researcher for further information about the study and possible inclusion, they will be contacted by phone, videoconferencing or in-person, depending on the preference of the patient. The researcher will inform them about participation and the consequences on being randomized to either the control or experimental condition. The researcher will clearly communicate that patients who are assigned to the control condition can still use an internet-based intervention after the study is finished. Furthermore, the researcher will clearly indicate that the decision to participate or drop out of the study will not affect their treatment or evaluation of their therapist. After informing the patient by means of a conversation and folder, the researcher will ask for their informed consent in participating. Next, the patient fills out the baseline assessment (T0) and is randomized to the control condition - which comprises forensic psychiatric treatment as usual (TAU) for aggression regulation, or the experimental condition, in which the internet-based intervention 'Aggression' is used as a supplement to TAU.

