## **8.2 Randomisation, blinding and treatment allocation**

Because blinding is impossible due to the use of the internet-based intervention in treatment, this study is a non-blinded RCT. After a participant is screened and has given informed consent, they will be randomized by the principal investigator. The randomization will be supported by an online tool (<https://sealedenvelope.com/>). Participants are not randomized per participating organization or clinic because there are major differences in the number of patients treated by these clinics. Instead, once a patient is included, they receive a participant number, which will be aligned with a random sequence of treatment allocations, i.e. participants are either allocated to the intervention or control group. The first participant included in the study is allocated according to the first treatment allocation on the list, the second participant according to the second allocation, and so forth.

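### Step 5 randomises directly after consent, against the baseline-first order stated elsewhere, and no visible text says randomisation waits for a late T0

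*Combined protocol and SAP*

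**What the plan says.** Four places in the protocol bear on the order of consent, T0 and randomisation.

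- Section 8.3, Step 5, headed "Randomization and start intervention – Week 12": "Directly after the patient has provided informed consent, the patient is randomized by the researcher". On the result it adds: "This is communicated to the therapist, who will let the patient know whether they will start with the intervention".
- Section 3.3, straight after describing consent: "Next, the patient fills out the baseline assessment (T0) and is randomized to the control condition".
- Section 8.3, Step 4, headed "Baseline assessment (T0) – Week 11", sets out its opening action as follows: "Before they start with the intervention - thus before they are allocated to a condition - all participants will be sent a link". Patients answer in their own time. Non-responders get an automated reminder after two days, a researcher's e-mail after five, and then a prompt from the therapist at the next session. If the questions prove too difficult, "the researcher will contact the patient and fill the questionnaires out together". If the patient declines for another reason, the therapist talks over whether they can stay in the study.
- Section 8.2: "After a participant is screened and has given informed consent, they will be randomized by the principal investigator".

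Consent is placed in Weeks 8-11 (Step 3). For the T0 week, 3.3 gives 12 and Step 4 gives 11. The Summary sets the later assessments at +6, +14 and +26 weeks from baseline; 3.3 and the step headings put them in weeks 17, 25 and 37. Step 7 also describes T2 as coming after 15 weeks. Section 3.3 has the module starting at about 12 weeks and at 14 at the latest.

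**The concern.** The trial is not blinded, the three main outcomes are self-reported, and the therapist tells the patient the arm. A T0 score given after that conversation is no longer a pre-allocation measurement, because knowing the arm could change how a patient rates self-efficacy, readiness or aggression. T0 is one of the four time points in the mixed model of section 10.1, where the group-by-time interaction is the test of interest. It is also subtracted in the T2-T0 and T3-T0 change scores of the engagement regressions in section 10.2. A mixed model can accommodate a missing T0, but it cannot repair one that was influenced by knowledge of the arm.

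There are two separate defects. Step 5 gives staff an instruction that, taken literally, puts T0 after randomisation. And even with Step 5 corrected, nothing visible tells staff to hold the allocation while T0 is being chased.

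**Working it through.** **1. Order, side by side.**

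| Place | Order given |
|---|---|
| 3.3 | consent, T0 filled out, randomised |
| 8.3 Step 4 | T0 link sent before allocation |
| 8.3 Step 5, heading | randomisation in Week 12 |
| 8.3 Step 5, text | randomised directly after consent |
| 8.2 | screening and consent come first; T0 not mentioned |

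The Step 5 text disagrees with 3.3 and Step 4. It also disagrees with its own heading for anyone who consents in Weeks 8-10. Section 8.2 is silent about T0; it allows T0 in between, so it does not conflict.

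**2. T0 week.** The plan's weeks reproduce from T0 in week 11: 11+6=17, 11+14=25, 11+26=37. From the week 12 given in 3.3 they do not: 12+6=18, 12+14=26, 12+26=38. Section 3.3 therefore disagrees with Step 4 and with its own intervals. Step 7's 15 weeks for T2, if counted from T0, gives 25-15=10, which matches neither.

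**3. How long T0 can stay outstanding.** Inputs: first reminder at day 2; e-mail at day 5, or 2+5=7 if the five days run from the first reminder (Step 4); weekly sessions (5.1.2). Assumptions: the therapist is contacted at once and no session is missed, so the next session is 0-7 days away. The therapist prompt then falls between day 5+0=5 and day 7+7=14 after the link.

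Take day 0 as the first day of week 11, so that week 12 is days 7-13, week 13 is days 14-20 and week 14 is days 21-27.

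| Link sent | Prompt, earliest (+5) | Prompt, latest (+14) |
|---|---|---|
| first day of week 11 (day 0) | day 5, week 11 | day 14, first day of week 13 |
| last day of week 11 (day 6) | day 11, week 12 | day 20, last day of week 13 |
| last day of week 12 (day 13) | day 18, week 13 | day 27, last day of week 14 |

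The last column gives upper limits, and completion with a researcher adds unstated time. The overlap with a Week 12 randomisation is possible, not certain.

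**4. Which estimates are exposed.** With complete data, the group-by-time contrast at visit t is (E_t - E_0) - (C_t - C_0), where E and C are the arm means. Suppose a share p of an arm's T0 scores is given after disclosure, with average shift d. The contrast then moves by -(p_E x d_E - p_C x d_C). The documents give neither p nor d for either arm, so neither size nor direction can be calculated. A between-group t-test at T3 uses E_3 - C_3, which contains no T0 term.

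**The case against.** The strongest reply is that the intended order is plain. Section 3.3 says T0 is filled out and then the patient is randomised, Step 4 says T0 precedes allocation, and the steps are numbered and dated that way. One sentence in Step 5 is out of line. Step 4's handling of non-completers ends with a discussion about staying in the study and sits before Step 5, which reads as pre-allocation handling. Week 12 is approximate, since 3.3 lets the module start as late as week 14. The late dates above also stack adverse choices: with a link on the first day of Week 11 and the e-mail five days after the link, the prompt falls on days 5-12, by Week 12 at the latest. Finally, the sample size rests on a t-test at T3, which does not need T0.

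All of this stands as a limit on the point. It does not remove the contradiction in an operative instruction, and it does not supply a rule that randomisation waits.

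A reader might infer more, and the documents do not support it:

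- That T0 will be collected after allocation. Sections 3.3 and Step 4 state the opposite intention.
- That 8.2 is a second contradiction. It lists prerequisites and leaves room for T0.
- That the later paragraph of 8.2, which lists T0 among questionnaires a therapist may be contacted about, foresees missing T0s after allocation. It is a generic list of all four assessments.
- That naming the principal investigator in 8.2 and the researcher in Step 5 is a conflict. They may be the same person.

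**Conclusion.** The point holds as a contradiction with a missing condition. Step 5's sentence is wrong against 3.3, Step 4 and its own heading; the T0 week is inconsistent on the plan's own figures; and no visible passage makes randomisation wait for a late T0. Confidence is high for these textual findings.

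The consequence is conditional. Only if Step 5 is followed literally, or if randomisation goes ahead while T0 is outstanding, could some T0 scores follow disclosure of the arm. The group-by-time interaction and the change scores would then be open to bias, while a comparison at T3 alone would not be. Neither the number of late T0s nor the size or direction of any bias can be estimated from the documents. The 5-14 day range assumes immediate contact with the therapist and no missed session. Figure 1 is not shown in this copy and could bear on the intended order. The correction should be made because it is cheap and protects the baseline of the main analysis.

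**What to change.** - Replace the Step 5 sentence with one sequence: consent, T0 submitted, then randomisation.
- State in 8.2 and in Step 5 that a submitted T0 is required before the allocation is drawn. Add that patients who never submit T0 are not randomised and do not count towards the 154.
- Reconcile 3.3, Step 4 and Step 7 to one T0 week and consistent intervals, and check Figure 1 against the result.
- As tidying only, remove T0 from the list of questionnaires chased after allocation in 8.2, and name the same randomising role in both places.

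The cost is wording; there are no new visits or data. The real downside is that late T0 responders are randomised later. On the upper limits above, the therapist prompt can come as late as the end of week 13 (link in Week 11) or week 14 (link in week 12). One missed weekly session adds seven days (20+7=27, 27+7=34), moving these to the end of weeks 14 and 15, and 3.3 itself says missed sessions are common. Some patients could therefore approach or pass the 14-week maximum start in 3.3. The sponsor must reconcile that limit with the new condition. Patients who never submit T0 would have to be replaced within the recruitment period.

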**Step 6: Mid-treatment assessment (T1) – Week 17**

In order to assess change during the intervention period, the three questionnaires to assess self-efficacy, aggression and treatment readiness are again administered to participants in the control and experimental group in week 17 of the study period. During treatment, the

therapist indicates that the patient can expect the questionnaires in the upcoming week to ensure that the link to the Qualtrics questionnaires is not overlooked. After that, the researcher e-mails the link to the Qualtrics questionnaires to the patient. If the patient did not complete the questionnaire after two days, a reminder is sent via e-mail. If the patient does not fill out the questionnaire after this reminder, the same procedure as in the baseline is followed.

Furthermore, the TWEETS is again administered, following the same procedures as at T0. Finally, participants will receive the first €10 voucher after completing the baseline assessment via e-mail.

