#### 4.4 Sample size calculation

This sample size calculation is conservatively based on the ability to detect at least a moderate effect of Cohen's  $d = .50$  on the primary outcomes at follow-up (T3). A power analysis was conducted with G\*power. The analysis was conducted with a moderate effect size of 0.5, a  $\beta$ -power of .8, a p-value of 5%, and an independent two-sided t-test as method of analysis. This analysis showed that 64 patients need to be included in each condition. This means that a total of 128 patients needs to be included. Accounting for a drop-out of 20%, the goal for inclusion is set at a total of 154 patients. It is important to note that participants in the experimental condition are considered as a 'drop-out' when they don't fill out the questionnaires at all measuring moments, not when they stop using the intervention. In other words: patients can stop using the intervention. In other words: patients can stop using the intervention, but can still complete their participation in the study if they fill out all questionnaires. Adherence to the intervention is not the same as drop-out from the study, since it is a different concept. The main reason for this is that earlier research has shown that patients often stop using these interventions before all lessons are completed, so it is not realistic to expect that all patients fully complete the intervention. In order to account for this, the number of completed lessons will be included as a moderator for effectiveness in the analyses to investigate whether adherence is related to effectiveness. Additionally, a sub-goal of this study is to determine whether engagement is a predictor of adherence and effectiveness to incorporate non-adherence to the intervention in the study. The intended 154 patients will be included at four different organizations that all have multiple forensic outpatient clinics.

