studies with this target group has shown that this can be an additional motivator for patients to participate. In all communication, these rewards will be mentioned to ensure that the patients are aware of the fact that they will be compensated for their invested time. To prevent that patients drop out during data collection, they will receive one voucher halfway, and one after completing all questionnaires. Additionally, when patients don't fill out questionnaires at one of the measurement moments, they will be reminded via e-mail and if that is not effective, the researcher will contact the therapist, who will remind the patient of the questionnaires. Sixth, in line with this, to prevent drop-out due to high time investment, the four selected questionnaires are kept as short as possible and filling them out will only take a couple of minutes. Also, data from risk assessment instruments that are already being administered is used to prevent additional time investment from patients and therapists. Seventh, as is the case with any internet-based intervention, patients might not be fully adherent, meaning that they do not complete the entire intervention. While this is a realistic risk, this does not threaten the feasibility of this study, because this is also an interesting and relevant result. If, even if therapists and patients receive much support in using the intervention, patients still do not complete the intervention, this has implications for its application in clinical practice. Additionally, adherence to the intervention will be used as a predictor for effectiveness to investigate if there is a dose-response relationship. It is important to emphasize that patients that do not fully complete the intervention, but still fill out all questionnaires, are not considered as a drop-out. Finally, it can be challenging to gather large sample sizes in forensic mental healthcare. To overcome this, data collection will take place in four organizations, that all have multiple outpatient clinics where patients can be included. The feasibility of including approximately 38 patients per organization – which all have multiple outpatient clinics - is elaborately discussed with representatives from the organizations that also participate in the project team that coordinates this study. Furthermore, initial contact with therapists has underlined the expectation that the intended number of participants can be reached.

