### ***Step 9: Follow-up assessment (T3) – week 37***

37 weeks after start of treatment, the three questionnaires (self-efficacy, aggression and treatment readiness) will be again administered via Qualtrics. If, at this point, the patient is not being treated at the outpatient clinic anymore, he or she will be contacted by the researchers. This will be clearly communicated in the informed consent form and by the therapist. The FARE that will be administered about 6 months after treatment as part of standard assessment by clinics will be used for the follow-up assessment. Participants will receive the second €10 voucher after completing the this final assessment.

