**8.4 Time investment of participants**

Participants in the experimental and control condition fill out three short questionnaires per measurement moment. This is estimated to take a maximum of 15 minutes. Data collection is kept short intentionally: forensic psychiatric patients are generally considered as hard to involve in research due to low motivation and short attention spans. To increase the feasibility of data collection, only the most relevant questionnaires from a clinical and research point of view are used. Additionally, patients in the experimental condition individually work on the intervention outside of in-person treatment sessions. On average, this is estimated to take about 30 minutes per weekly lesson, but experiences in practice show that this can either take much longer or shorter, depending on the patient and lesson. Furthermore, to increase the feasibility of this study, participants will be compensated for their invested time by means of a voucher of €10 after the mid-treatment assessment (T1) and another voucher of €10 the final post-treatment assessment (T3). Experience with research with this target group has shown that financial rewards can serve as a motivator to participate and complete the study.

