### **8.6 Replacement of individual subjects after withdrawal**

To account for withdrawal of subjects, 20% more participants than required according to the power analysis will be included. If patients drop-out, this will be accounted for due to this extra 20%. Patients are considered as a drop-out if they stop filling out the questionnaires before the end of the study. Consequently, if patients stop using the intervention but still fill out the questionnaire, they are not considered a drop-out. A reason for this is that investigating whether non-adherence to these interventions is problematic and related to engagement or effectiveness is part of this study. Data collection will be ended after including the intended 154 patients. If throughout the study, there are signs that more than 20% of the patients drop out, the researchers will re-evaluate the feasibility of the data collection with participating therapists and search for points of improvements.

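### A patient unwilling to complete T1 or T2 is sent through the baseline non-response procedure after randomisation, and conflicting drop-out and voucher rules leave it unclear whether that patient's T3 score is still sought

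*Combined protocol and SAP*

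**What the plan says.** **Non-response.** Section 8.3, Step 4 sets the T0 procedure:
- an automated reminder after two days and a researcher e-mail after five;
- then contact through the therapist, who asks for the reason;
- if the questions are too difficult, the researcher completes them together with the patient;
- if the patient does not want to answer for some other reason, "the therapist will discuss if participation in the study is still an option".

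Step 6 extends this to T1: "If the patient does not fill out the questionnaire after this reminder, the same procedure as in the baseline is followed". Step 7 refers back to the same procedures for T2.

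**Drop-out.** Section 4.4 says that participants in the experimental condition are "considered as a 'drop-out' when they don't fill out the questionnaires at all measuring moments". Section 8.6 says: "Patients are considered as a drop-out if they stop filling out the questionnaires before the end of the study".

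**Vouchers.** Section 4.5 says of patients that "they will receive one voucher halfway, and one after completing all questionnaires". Step 6 says that "participants will receive the first €10 voucher after completing the baseline assessment via e-mail", whereas sections 8.4 and 11.6 place that voucher at T1. For the second voucher, Step 9 says "Participants will receive the second €10 voucher after completing the this final assessment", and section 8.4 agrees. Section 11.6 first ties it to T3, then speaks of compensation for patients who complete every questionnaire.

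**The concern.** At T0, asking whether an unwilling patient should take part is reasonable, because Step 4 places that assessment before allocation. After randomisation the same talk concerns a patient who belongs to the intention-to-treat comparison. It is held by a therapist who has been told the arm (section 8.2; section 8.3, Step 5) and who, in the experimental condition, also delivers the intervention. The subject of the talk is the whole study, not the one questionnaire that was missed.

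Section 4.4 sizes the trial on T3, and section 10.1 calls the intervention effective only on the strength of T3 results. The planned mixed model can use a patient who lacks T1 or T2, so such a patient's T3 score keeps its value. Conduct rules should protect that score. Here they leave open whether it is pursued, whether the patient already counts as lost, and whether any payment remains to be earned.

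**Working it through.** No power calculation settles this point. The check is to follow one patient through the rules and compare the sections.

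**1. Is T3 sought after a missed T1 or T2?**
- Section 8.3, Step 9 sends T3 without making it conditional on earlier answers. Researchers contact patients who are no longer treated at the clinic.
- Section 4.5 describes non-response at any one assessment as leading to reminders only.
- Section 8.2 mentions contact with the therapist about non-response at any of the four assessments, in its text on the control condition.
- None of these cancels T3 after a missed wave. None says that T3 is still sought after a refused T1 or T2 and the talk that follows.

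**2. Who is a drop-out?** The phrase in section 4.4 can mean missing any assessment or missing all of them. The sentences that follow there equate completing participation with filling out every questionnaire, which favours the first meaning.

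| Assessments answered | 4.4, any-missed reading | 8.6 |
|---|---|---|
| T0, T1, T2, T3 | not a drop-out | not a drop-out |
| T0, T2, T3 | drop-out | not a drop-out |
| T0, T1, T3 | drop-out | not a drop-out |
| T0, T1, T2 | drop-out | drop-out |

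Section 4.4 also gives no definition for the control condition.

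**3. Does the definition matter?** The plan's figure reproduces: 64 × 2 = 128, and 128 × 1.20 = 153.6, rounded up to 154. The same 20% is the trigger in section 8.6 for re-evaluating feasibility. The documents give no miss rate per assessment. Assume for illustration an independent miss rate p at each of T1, T2 and T3:
- any-missed share = 1 − (1 − p)³;
- share without T3, which is how 8.6 would count = p.

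| Assumed p | Any-missed share | Of 154 | Without T3 | Of 154 |
|---|---|---|---|---|
| 5% | 1 − 0.95³ = 14.3% | 22 | 5% | 8 |
| 7% | 1 − 0.93³ = 19.6% | 30 | 7% | 11 |
| 10% | 1 − 0.90³ = 27.1% | 42 | 10% | 15 |

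At p = 7% one definition has used up almost all of the 20%, and the other about a third of it. At p = 10% only one of them trips the trigger. This table shows how far the two counts differ. It does not estimate T3 data lost because of the rules.

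**4. What is paid?** Take a patient who answers T0, T2 and T3 but misses T1.

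| Voucher 1 depends on | Voucher 2 depends on | Total |
|---|---|---|
| baseline (Step 6) | T3 (Step 9, 8.4, 11.6) | €10 + €10 = €20 |
| baseline | all questionnaires (4.5, 11.6) | €10 + €0 = €10 |
| T1 (8.4, 11.6) | T3 | €0 + €10 = €10 |
| T1 | all questionnaires | €0 + €0 = €0 |

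One patient can be owed anything from €0 to €20. Under the all-questionnaires condition, a patient who missed T2 has nothing left to earn at T3. Under the T3 condition €10 remains.

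**The case against.** The strongest reply is that this is loose wording around a procedure meant to retain patients. Most of the T0 procedure consists of reminders and help with completion. The talk arises only when a patient is unwilling for another reason, and it is a discussion, not a removal. The drop-out wording in section 4.4 serves the sample-size allowance, and no section removes a patient because of it. Analysis is by intention to treat, with a model that is said to handle missing data. The all-questionnaires phrase in section 4.5 may indicate only timing, the matching sentence in section 11.6 contrasts questionnaires with use of the intervention, and the baseline reference in Step 6 looks like a slip.

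All of this stands, and it rules out three stronger conclusions that a reader might draw:
- **That a missed T1 or T2 takes the patient out of the study.** No section says so, and Step 9 does not make T3 conditional.
- **That the second voucher is lost.** That follows from one of two conflicting conditions, and three statements tie payment to T3.
- **That a particular loss of power, or a difference in loss between arms, follows.** The miss rates would have to be invented. Subtracting such patients on top of the planned 20% could count them twice. The same procedure applies to both arms, so a difference by arm is possible but not shown.

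The reply does not remove the gap. Staff still have two drop-out definitions, two conditions for each voucher, and no instruction on T3 after a refusal.

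**Conclusion.** The point holds as a defect in the conduct rules. After randomisation an unwilling patient meets a talk about study participation with a therapist who knows the arm, and the plan does not say that T3 is still sought. The drop-out definitions in sections 4.4 and 8.6 classify the same patient differently, and the voucher conditions contradict each other across sections 4.5, 8.3, 8.4 and 11.6. These rules may discourage some patients from giving the T3 score, in a population that the plan itself describes as hard to involve in research. That effect is an inference from the text, and its size cannot be derived from the documents. The contradictions rest on the wording alone, except that the drop-out conflict needs the any-missed reading of section 4.4. The change is worth making because it costs almost nothing and protects the time point that matters most.

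**What to change.** - **Section 8.3:** state that after randomisation a missed or refused questionnaire ends only that assessment, that T2 and T3 links still go to every randomised patient who has not withdrawn from the study, and that the participation talk applies at T0 only.
- **Sections 4.4 and 8.6:** use one drop-out definition for both arms, for example the absence of a T3 questionnaire.
- **Sections 4.5, 8.3 (Step 6) and 11.6:** pay the first voucher for T1 and the second for T3, whatever was missed earlier, in line with section 8.4. Make the patient information match.
- **Sections 8.5 and 8.7:** reconcile the statement on continuing to T3 with the withdrawal rule and with the exclusion of patients who leave treatment. Step 9, which contacts patients no longer treated at the clinic, needs to fit as well.

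The cost is editing these sections and the patient letter, plus a few more €10 vouchers and questionnaire links. The sample size and the analysis model do not change.
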